6 SCHEDULE OF ASSESSMENTS

6.1 PK Cohort

Assessment	Screening	Baseline/ Procedure	Day 1	Day 3	Day 7 (±2 d)	Day 14 (±2 d)	Day 21 (±2 d)	Day 30 (±3 d)
Informed consent	X							
Medical/surgical history	X							
CT scan (≤ 30 days prior to enrollment)	X							
Blood sample collection (~11 ml)		X ^a	X ^b	X ^b	X ^b	X ^b		X ^b
24-hour urine collection		X ^c	X ^c					
In-office bilateral FSO dilation		X						
Endoscopic grading and recording	X	X ^d			X	X	X	X
Sino-Nasal Outcome Test (SNOT-22)		X ^d				X		X
Concomitant medications	X	X	X	X	X	X	X	X
Adverse event reporting	X	X	X	X	X	X	X	X
Urine pregnancy test (female subjects of childbearing potential)	X ^{e,f}	X ^{e,f}						
Documented birth control (female subjects)			X	X	X	X	X	X

Abbreviations: CT, computed tomography; d, days; FSO, frontal sinus ostium/ostia; min, minutes; ml, milliliter.

- ^a. Blood draws to occur at baseline, before balloon dilation procedure and again at Hour 0.5 (±5 min), 1 (±5 min), 2 (±10 min), and 4 (±15 min) after the end of baseline procedure
- ^b. All blood draws should occur in the morning and at approximately the same time of the day during the follow-up visits. Day 1 blood draw to occur 24 hours (±3 hours) after the baseline procedure. Day 3 blood draw to occur 72 hours (±3 hours) after the baseline procedure
- ^c. Urine samples will be collected for a 24-hour duration prior to the baseline visit (pre-procedure) and for a 24-hour duration following the baseline procedure (post-procedure)
- ^d. All endoscopic assessments and SNOT-22 performed prior to the baseline procedure, except for the FSO diameter, which must be performed before and after the balloon dilation procedure.
- ^e. Female subjects with reproductive potential are required to undergo a urine pregnancy test at screening and prior to the baseline procedure.
- ^f. Female subjects are required to confirm their nursing status at screening and baseline

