11 SUBJECT TREATMENT AND STUDY PROCEDURES

11.1 Screening Phase

Pre-screening

During the pre-screening phase, clinical investigators or designees will perform an initial evaluation of potential candidates for study eligibility. This initial pre-screening phase may include review of existing patient information (e.g., previously performed diagnostic measures, medical history, sinus endoscopies, sinus surgery).

Consent, enrollment, and screening

If the patient appears to be a potential candidate for the study based upon existing information, written informed consent will be obtained. No protocol required testing will be performed solely for the purposes of this study prior to obtaining patient written informed consent.

Clinical investigators or designees will approach the patient to obtain written informed consent. The background of the proposed study, the dilation procedure, the follow-up schedule and all potential risks and benefits will be carefully explained to each patient. The clinical investigator or designee obtaining the informed consent shall:

- Avoid any coercion of or undue influence of patients to participate,
- Not waive or appear to waive patient's legal rights,
- Use language that is non-technical and understandable to the patient, and
- Provide ample time for the patient to consider participation.

Each patient must sign and date the informed consent form (ICF) approved by an appropriate Institutional Review Board (IRB) and the sponsor. Patients are considered enrolled in the study upon signing the IRB-approved ICF. Enrolled subjects will be assigned unique identifying codes by the Electronic Data Capture (EDC) system and entered into the study database. Upon enrollment, subjects will have a screening assessment.

The screening assessment for both cohorts will include:

- CT scan (must be performed within 30 days prior to enrollment in the PK cohort and prior to randomization in the randomized cohort),
- Endoscopic examination, grading and video recording,
- Female subjects of reproductive potential must confirm their nursing status, undergo a urine pregnancy test, and be informed about acceptable birth control methods as part of the screening assessment and again at baseline.

PK cohort subjects who pass the screening assessment will be asked to collect urine samples for a 24-hour duration prior to the baseline visit.

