11.2 Baseline/Procedure Phase

Baseline assessment

Upon meeting eligibility requirements, subjects in both cohorts will undergo a baseline endoscopic examination, including grading and video recording.

Female subjects of childbearing potential will undergo a urine pregnancy test prior to the baseline procedure and be required to use acceptable contraceptive method(s) during the entire duration of the study follow-up. Acceptable methods of contraception may include:

Established use of oral, injection or implantable hormonal contraceptives;

- Double-barrier methods (i.e., intra-uterine devices) and barrier contraceptives (i.e., condom, diaphragm or cervical/vault caps) used with spermicide (foam, gel, film, cream or suppository);

- Female sterilization (e.g., tubal occlusion, hysterectomy or bilateral salpingectomy); or
- Vasectomized male partner, if the sole partner for the subject.

Note: The baseline endoscopic assessment and pregnancy testing must be performed before the dilation procedure.

PK cohort: Baseline assessment will also include:

- SNOT-22 questionnaire.
- A blood sample collection prior to the baseline procedure.
- Instructions for urine sample collection through 24 hours after the baseline procedure
 - Urine collection starting with the void after the procedure through 24 hours on following day.

Subject preparation for baseline procedure

Subjects will be prepared for the baseline procedure per investigator's standard protocol used for nasal endoscopy. The topical anesthesia regimen may consist of:

- Spraying the nasal cavity with 4% lidocaine (or equivalent, such as pontocaine) with oxymetazoline (or equivalent) nasal decongestant spray;
- Placing cotton pledges soaked in lidocaine (or equivalent) and oxymetazoline (or equivalent) solution against the inferior turbinate, and into the ethmoid sinus (if available in the clinic setting, topical cocaine may be used); and
- Injecting into the sinus tissue and/or polypoid tissue with lidocaine (or equivalent) as necessary.

The anesthesia period should be as long as necessary to ensure complete numbness of the subject's septum and middle turbinate. Once properly anesthetized, subjects may undergo the baseline procedure.

Baseline procedure

All UP Devices will be provided by the study sponsor and must be used according to the instructions for use (IFU). Subjects will undergo bilateral in-office dilation of the FSO with the study UP Device.

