8. Reposition the balloon distal to the first inflation site such that the proximal half of the balloon is in contact with sinus mucosa, adjacent to the first inflation site.
9. Repeat steps 5 and 6 to dilate the sinus ostium for a total of 2 inflations in each sinus ostium.
10. Retract the deflated balloon into the guide catheter before removing the dilation system out of the nostril (Note: Do not retract the tip of the UP Device beyond the blue tip marker on the guide catheter to prevent loss of the drug).

PK cohort: Subjects will undergo in-office bilateral sinus dilation with the UP Drug-Coated Device in the frontal sinuses with 2 inflations per sinus (total of 4 inflations per Device).

- Repeat steps 1 through 10 for each FSO with the same UP Drug-Coated Device. Note: Dilation of the maxillary and/or sphenoid sinus with the same UP Device may be performed, if clinically necessary. However, dilation of the maxillary and/or sphenoid sinuses must be performed only after dilation of the frontal sinuses.
- On the day of the baseline procedure, 4 additional blood draws (~ 11 ml at each timepoint) will be performed at 0.5 (\pm 5 min), 1 (\pm 5 min), 2 (\pm 10 min) and 4 (\pm 15 min)

hours following the end of the baseline procedure, defined as removal of UP Device from the nostril after successful dilation of both FSO in each subject.

Randomized cohort: Subjects will undergo an in-office sinus dilation with the UP Drug-Coated Device of the FSO randomized to treatment (2 inflations per device) while the contralateral FSO will serve as control and undergo sinus dilation with a UP Control Device (2 inflations per device).

- Steps 1 through 10 will be followed with each frontal side dilated with the assigned UP Device.

Postoperative care

PK cohort subjects will be required to collect urine samples for 24 hours following the baseline procedure.

After the baseline procedure, subjects in the PK cohort will be allowed and subjects in the randomized cohort will be required to use saline sprays/rinses/irrigations starting Day 2.

PK cohort subjects will not be allowed to use INCS sprays throughout the 30 days follow-up duration. Randomized cohort subjects will be allowed to use INCS sprays starting after the scheduled Day 14 study visit, if medically necessary.

Device disposal

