9.3.1 PK Cohort

Data from the pharmacokinetic (PK) assessments of plasma MF, plasma cortisol, and 24-hour urinary cortisol concentrations, endoscopic and SNOT-22 scores will be expressed using descriptive statistics, including but not limited to, means, SD, medians, ranges and, where appropriate, coefficient of variation (%). The PK and cortisol parameters, C_{\max} , C_{24} , T_{\max} , and AUC_{0-24} will be calculated by non-compartmental methods according to the definitions below. Nominal sample times will be used in the calculation of all parameters.

C_{\max}	Maximal concentration after the baseline procedure.
T_{\max}	Time at which maximal concentration after the baseline procedure
C_{24}	PK and cortisol concentration 24 hours after the baseline procedure.
AUC_{0-24}	Area under the concentration-time curve from time 0 to 24 hours. The linear/log trapezoidal rule will be used.

Measurement of urinary cortisol excretion for 24 hours prior to the baseline procedure and for 24 hours after the baseline procedure will be analyzed using a validated bioanalytical method with a LLOQ of 1.00 ng/mL.

A_e	The amount of cortisol excreted in urine, will be calculated by multiplying the volume of urine collected over the 24-hour period by the concentration of cortisol measured in the urine sample.
ΔA_e	The change in cortisol urine exposure following administration- calculated as A_e for the 24 hours after baseline procedure minus A_e for the 24 hours prior to the baseline procedure.

The 24-hour urinary cortisol data will be tabulated for each subject for whom amounts are quantifiable.

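### The post-procedure urine collection opens with the first void after dilation and no void is required just before it, so ΔAe can include pre-dose cortisol and understate suppression

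*Protocol*

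**What the plan says.** **Post-procedure collection.** The only void rule is in Protocol 11.2, under the PK cohort's baseline assessment: "Urine collection starting with the void after the procedure through 24 hours on following day". Further on in 11.2, under postoperative care, only a duration is given: "PK cohort subjects will be required to collect urine samples for 24 hours following the baseline procedure". Footnote c of the schedule (Protocol 6.1, repeated in SAP Appendix A) also gives only a duration.

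**Pre-procedure collection.** Protocol 11.1 says "PK cohort subjects who pass the screening assessment will be asked to collect urine samples for a 24-hour duration prior to the baseline visit". Footnote c also places its end at the baseline visit. Protocol 4 (safety evaluation), 9.2.3 and 14.1, and SAP 6.3.1 and 9.3.1, count the 24 hours back from the baseline procedure instead. No section says which void opens or closes this collection.

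**Between arrival and dilation.** Protocol 11.2 places endoscopy with grading and video, SNOT-22, a blood draw, anesthesia for as long as needed, and probing of both ostia in this period. It does not ask subjects to empty the bladder before dilation. The nearest provision applies to some subjects only and sets no time: "Female subjects of childbearing potential will undergo a urine pregnancy test prior to the baseline procedure".

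**Analysis.** In SAP 9.3.1, Ae "will be calculated by multiplying the volume of urine collected over the 24-hour period by the concentration of cortisol measured in the urine sample". ΔAe, described as "The change in cortisol urine exposure following administration", is the post-procedure Ae minus the pre-procedure Ae. There is no term for the actual length of either collection.

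**The concern.** Urine passed at a given void was formed since the previous void. If the first void after dilation is kept and the previous void came well before dilation, the post-procedure sample contains some pre-dose cortisol. The amount labelled as 24 hours after the procedure then covers those 24 hours plus the gap. Subtracting a nominal 24-hour pre-procedure amount leaves the extra in ΔAe, which makes suppression look smaller. The gap can also differ between subjects, because only women of childbearing potential must give urine before the procedure.

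At stake is a systemic safety measure in a first-in-human cohort of 5 subjects without a control group, where each subject's own before-and-after comparison carries the information. SAP 9.3.1 also derives plasma cortisol AUC0-24, so ΔAe is not the only integrated cortisol measure. It is the only one with a 24-hour pre-dose comparator. Plasma cortisol has one pre-procedure sample, and none is drawn between 4 and 24 hours after dilation.

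**Working it through.** The documents state no expected ΔAe, excretion rate, void time or suppression threshold, so there is no figure of the plan's own to reproduce. A mass balance shows the size.

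**Inputs.** From the documents: the opening rule in Protocol 11.2 and the definitions of Ae and ΔAe in SAP 9.3.1. Assumed, because the documents do not give them:
- g: hours from the last void to dilation (0 to 4)
- m: excretion rate in that gap divided by the 24-hour mean rate (1 = flat)
- s: true proportional fall in cortisol excretion over the 24 hours after dilation

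**Formula.** Set the true pre-procedure 24-hour amount to 1. If the first void is kept and collection ends 24 h after the procedure:
- post-procedure Ae = m·g/24 + (1 − s)
- ΔAe = m·g/24 − s, so the bias is +m·g/24

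**Flat rate (m = 1).**

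| g (h) | Carry-over g/24 | True 20% fall reads as | True 50% fall reads as |
|---|---|---|---|
| 0 | 0% | 20.0% | 50.0% |
| 1 | 4.2% | 15.8% | 45.8% |
| 2 | 8.3% | 11.7% | 41.7% |
| 4 | 16.7% | 3.3% | 33.3% |

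**Higher rate in the gap (m = 1.5, assumed).** At 2 h the carry-over is 1.5 × 2/24 = 12.5%, and a true 20% fall reads as 7.5%. At 4 h it is 25.0%, and the same fall reads as a 5.0% rise.

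**Other readings of the same instruction, for a true 20% fall at m = 1.**
- *First void kept, clock runs 24 h from that void* (assumed 1 h after dilation, g = 2): 2/24 + 0.8 × (1 + 1/24) − 1 = −8.3%.
- *First void marks the start and is discarded* (1 h after dilation), collection ending 24 h after the procedure: 0.8 × (1 − 1/24) − 1 = −23.3%. The bias reverses. At m = 2 it is 0.8 × (1 − 2/24) − 1 = −26.7%.
- *Pre-procedure collection carries an equal extra void:* (m·g/24 + 1 − s) − (1 + m·g/24) = −s. The carry-over cancels in ΔAe.
- *No closing void at 24 h:* urine still in the bladder is lost, which lowers the post-procedure amount and makes suppression look larger.

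**The case against.** The strongest reply is that the direction of the error is not established. The first void could be read as starting the clock only. The pre-procedure collection has no opening or closing rule, so its amount may carry its own extra void. Where the text counts back from the procedure rather than the visit, that collection may run up to dilation, which shortens or removes the gap. A subject who happens to void just before dilation contributes no carry-over. With no closing void specified, there is also a possible loss at the other end. All of this stands, and it makes the bias conditional.

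It can also be said that nothing depends on ΔAe. PK success is at least 80% of attempted ostia dilated with no USADE. Urinary cortisol is tabulated descriptively without a test or threshold, and plasma cortisol is measured over the same 24 hours independently of voids. This is correct and limits the weight of the point.

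The objection does not remove the defect. The one void rule that the plan states, taken in its ordinary sense, does not line up with dosing, and no other section corrects it. If the sign of the error depends on how a site reads one line, that is itself a reason to settle the line.

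**Conclusion.** The point holds in conditional form. Followed as ordinarily read, Protocol 11.2 lets pre-dose cortisol into the post-procedure sample, and SAP 9.3.1 makes no allowance for it. At an assumed gap of 1 to 2 h and a flat rate, the carry-over is about 4% to 8% of daily excretion. At 4 h it is 16.7%, which takes most of a true 20% fall out of view. The gap and the rate are assumptions, and the table also assumes a clean pre-procedure amount and a complete collection to 24 h.

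A reader might infer that the collection always includes pre-dose cortisol, that the error always runs one way, or that suppression is hidden. The documents do not support these readings. Carry-over can be zero, can cancel, or can be replaced by a bias of opposite sign, and a large fall would still show: a true 50% fall reads as 33.3% even at 4 h and a flat rate. The supportable finding is that the opening and closing voids of the two collections are not tied to the time of dilation, so a descriptive safety measure can be attenuated by an amount that the planned analysis neither records nor corrects. It should be fixed, but no success criterion is affected.

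**What to change.** In Protocol 11.2 and in footnote c (Protocol 6.1 and SAP Appendix A):
- Require a timed void immediately before dilation and exclude it from the post-procedure collection.
- Collect every later void, and end with a closing void at 24 h.
- Define the first and last voids of the pre-procedure collection in the same way, and settle whether it ends at the baseline visit or the baseline procedure, using one term in all the sections listed above.
- Record the start and stop times of both collections.

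In SAP 9.3.1, compute Ae over the recorded interval, normalised to 24 h: volume × concentration × 24 / recorded hours. With g = 0 and a closing void at 24 h, ΔAe equals −s in the mass balance above.

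The cost is one instruction to sites and subjects and a few recorded times, with no extra visit or blood sample. The PK cohort enrolls first, and the documents do not say whether its collection is finished. If it is, check whatever void times were recorded and report the limitation beside ΔAe.

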7.2 Investigational Device

Intended use

The UP Drug-Coated Device is intended to dilate and locally deliver steroids to the frontal sinus ostia to maintain patency in patients ≥ 18 years of age.

Device description

The UP Drug-Coated Device and the UP Control Device (hereafter referred to as “UP Device”) are over-the-wire sinus balloon catheters with a balloon at the distal end (with or without MF-coating). **Figure 1** depicts a schematic representation of the UP Device. On the proximal end of the device, there are two primary ports: the first port is compatible with an inflation device that is used to inflate the balloon with saline for sinus dilation; and the second port is intended to be used with a compatible lightwire and guide catheter to confirm access into the target sinus. The usable working length is 207 mm.

[figure not shown]

Figure 1: Schematic of the UP Device

Balloon catheter

The UP balloon catheter is shown in **Figure 2** and comprises a nylon balloon and distal shaft with markers to denote balloon distance from the guide catheter. The shaft markers on the distal end of the catheter aid in proper placement. The yellow marker denotes the proximal end of the balloon and the white markers are spaced 1 cm (single band) and 2 cm (double band) away from the proximal end of the balloon. The UP Device has a softatraumatic distal tip. The balloon diameter is 6 mm in diameter and the 20 mm of working length when inflated to a pressure of 12 atmospheres (atm).

[figure not shown]

Figure 2: Schematic of the UP Balloon Catheter

Balloon coating

UP Drug-Coated Device: The coating on the balloon of the UP Drug-Coated Device contains 3000 mcg of mometasone furoate (the active ingredient) in a polymer matrix of polyethylene glycol and polysorbate (inactive ingredients). The coating on the balloon is hydrophilic and designed to provide immediate release of MF during dilation into the apposing sinus mucosa. The device locally delivers drug to the treated sinus ostia to reduce edema/inflammation following sinus dilation.

UP Control Device: Similar to the UP Drug-Coated Device, the UP Control Device is an over-the-wire sinus balloon catheter. The UP Control Device does not contain drug and is identical to the UP Drug-Coated Device with respect to dimensions of the balloon.

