In order to support the safety of the UP Drug-Coated Device with 3000 mcg of MF, a pharmacokinetic (PK) simulation was performed using published human plasma MF PK concentrations, following an intravenous (IV) administration of 400 mcg of MF and a simulated absorption process from the sinus following nasal administration of MF. Available human PK data for the approved MF products (specifically a dry-powder inhalation [DPI] administration of Asmanex[®]) and supportive data from MF plasma concentration-time profiles generated with the UP Drug-Coated Device were used for comparison. Predicted AUC values with MF from the UP Drug-Coated Device (459-1376 pg.hr/ml) were similar to those reported for the approved daily doses of up to 880 mcg of MF administered as DPI and metered dose inhalation (MDI) (93-1383 pg.hr/ml). Predicted C_{max} ranges for the UP Drug-Coated Device (105-315 pg/ml) overlapped with the C_{max} ranges reported for approved doses of DPI and MDI (35.2-189 pg/ml) but were higher for those simulations which assumed a higher fraction of dose delivered (90%) or at higher (2%) bioavailability than observed for approved products. The predicted MF exposures (AUC and C_{max}) from the 3000 mcg UP Drug-Coated Device are comparable to observed MF exposures described in publicly available documentation at doses up to 1600 mcg/day (*Data on file at Intersect ENT*).

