Prior to the baseline sinus dilation procedure, the FSO will be assessed under endoscopic visualization and the assessment will be recorded on the Endoscopic Scoring Form. Using a 3-mm olive-shaped frontal sinus suction tip, the patency and FSO diameter assessments will be performed. Final subject eligibility will be confirmed based on bilateral stenosis of the FSO on endoscopic assessment. NOTE: Physician may use light-assisted or image-guided instrument such as a smaller diameter frontal sinus seeker tip to confirm access of each FSO and if the sinus is amenable to balloon insertion.

No other devices, spacer, or packing (with or without steroid) may be used during or after the baseline dilation procedure. Aggressive suction and irrigations of the treated site should be avoided, as much as possible.

In subjects in the PK cohort, dilation of the maxillary and/or sphenoid sinus with the same UP Device may be performed, if clinically necessary, after the index dilation procedure. In subjects in the randomized cohort, dilation of the maxillary and/or sphenoid sinus with a commercially available balloon sinuplasty device may be performed, if clinically necessary, prior to randomization. No other surgical procedures at baseline will be allowed.

The steps to be followed for the in-office dilation procedure for this study are as follows:

1. Insert a compatible lightwire through the proximal end of the UP Device.
2. Insert the UP Device into the compatible sinus guide catheter.
 - a. If desired, attach the compatible sinus guide catheter handle to the sinus guide catheter before insertion of the UP Device.
3. Insert the sinus guide catheter into the FSO and position the sinus guide catheter tip opening toward the FSO (See **Section 7.2 Investigational Device** for compatible accessory devices).
4. Confirm that the lightwire is in the sinus, then advance the UP Device through the guide catheter and position it in the targeted FSO. Note: Under endoscopic visualization, ensure that the proximal end of the balloon (yellow single-band marker) is visible outside of the frontal sinus ostium.
5. Inflate the balloon of the UP Device with the compatible inflation device to 12 atmospheres (atm).
6. Hold the inflated balloon at 12 atm for a minimum of ~10 s and maximum of ~30 s.
7. Deflate the balloon.

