17.3.2 Blinding

The treatment and control devices are randomly designated with a device code (e.g.: Device C and Device D) and do not contain any identifying information regarding the treatment or control device. The information inside the randomization envelope will indicate which frontal sinus side receives which device code (e.g.: C or D). After the first side is treated with the assigned device, that device will be discarded before opening the device assigned to the contralateral side, so that no side-by-side comparison of the two devices is made by the clinical investigators or clinical staff.

Hence, the following personnel will be blinded to treatment assignment:

- Research coordinators at the site who have various responsibilities in conducting the study including assisting in baseline dilation procedure, handling randomization assignment, maintaining investigational product accountability records, and complete AE reports.
- Sponsor representatives who serve as a resource and provide guidance for clinical investigators and clinical staff on procedure with the investigational devices or during patient follow-up.
- Clinical Research Associates from Intersect ENT and its sub-contractors (as needed), who perform routine monitoring activities.
- The independent reviewer who will grade the Day 14 and Day 30 videoendoscopies.

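### Randomized cohort: a new guide catheter is not required for the second side and the side order is neither set nor recorded, so drug may reach the control ostium and order may be tied to device

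*Protocol*

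**What the plan says.** **Retraction.** Protocol 11.2 lists ten procedure steps that apply to both devices. Step 10 reads: "Retract the deflated balloon into the guide catheter before removing the dilation system out of the nostril". A note in that step adds: "Do not retract the tip of the UP Device beyond the blue tip marker on the guide catheter to prevent loss of the drug". Protocol 7.2 describes the coating as hydrophilic and "designed to provide immediate release of MF during dilation into the apposing sinus mucosa".

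**What changes between sides.** Protocol 17.3.2: "After the first side is treated with the assigned device, that device will be discarded before opening the device assigned to the contralateral side". The stated reason is blinding: "so that no side-by-side comparison of the two devices is made by the clinical investigators or clinical staff". The device-disposal paragraph of Protocol 11.2 sends investigational and accessory devices to biohazard waste but does not say when. For the randomized cohort, the same ten steps are followed on each side with the assigned device. No new guide catheter is mentioned.

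**Order.** The envelope is opened after anaesthesia and the final eligibility check (Protocol 17.3.1). It shows which side receives which code letter (Protocol 17.3.2; SAP 9.1). Neither document says which side or letter goes first, that order is randomised, or that it is recorded.

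**Analysis.** The primary test is a paired t-test on the treatment-minus-control difference in Day 30 patency grade, with no term for order (Protocol 16.3; SAP 10.3.2).

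**The concern.** The primary endpoint is a contrast between two sides of the same subject, so it is valid only if the sides differ in the assigned device and in nothing else that is linked to it. Two gaps bear on this.

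- **Carry-over.** If the coated side is done first and the same guide catheter is then used on the other side, the control ostium may receive some mometasone. That shrinks the measured difference.
- **Order.** Left/right assignment is randomised 1:1, which protects against left/right differences. It protects against first/second differences only if the order does not follow the device. A site that always starts with the same letter treats drug and control in the same sequence in every subject. Any first/second-side effect then becomes part of the estimated drug effect. If order is not recorded, this cannot be checked afterwards.

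**Working it through.** **1. Does the text exclude reuse of the guide catheter?** Following the same ten steps on each side does not imply new equipment: the PK cohort repeats those steps on the second side with the same drug-coated device. The discard rule in 17.3.2 names the UP Device and serves blinding. The disposal rule gives no timing. Both sides are frontal, and Protocol 7.2 lists one guide type (70°) for the device. Reuse is therefore not stated, but nothing in these documents rules it out.

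**2. The plan's own sample size.** Inputs from Protocol 16.2 and SAP 9.4.2: difference 0.5, SD of the difference 1.1, two-sided α 0.05, power at least 90%. For a paired t-test the noncentrality is (δ/σ)√n = (0.5/1.1) × √53 = 3.31 on 52 degrees of freedom. Power is 0.901 at n = 53 and 0.895 at n = 52, so the stated 53 is reproduced. Protocol 16.2 mentions a 1-sided test, but one-sided 0.05 would need only 43, so 53 is the two-sided figure.

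**3. Carry-over (sizes assumed).** Let *f* be the share of subjects treated coated-side first and *c* the fraction of the effect lost in them. Then δ = 0.5 × (1 − *fc*) and SD = √(1.1² + *f*(1 − *f*)(0.5*c*)²). For *f* = 0.5 and *c* = 0.1: δ = 0.5 × 0.95 = 0.475 and SD = 1.1003.

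| Effect lost, *c* | δ if *f* = 0.5 | Power, n = 53 | δ if *f* = 1 | Power, n = 53 |
|---|---|---|---|---|
| 0 | 0.500 | 0.901 | 0.500 | 0.901 |
| 0.1 | 0.475 | 0.870 | 0.450 | 0.832 |
| 0.2 | 0.450 | 0.831 | 0.400 | 0.738 |
| 0.3 | 0.425 | 0.786 | 0.350 | 0.623 |
| 0.5 | 0.375 | 0.677 | 0.250 | 0.369 |

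**4. Order (sizes assumed).** Let *q* be the share treated coated-side first and *o* the first-minus-second-side effect in grades. The bias in the mean difference is (2*q* − 1)*o*, and SD = √(1.1² + 4*q*(1 − *q*)*o*²). With no drug effect, the chance of a significant result favouring the coated device at n = 53 is:

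| *o* | *q* = 0.5 | *q* = 0.75 | *q* = 1 |
|---|---|---|---|
| 0.1 | 0.025 | 0.051 | 0.095 |
| 0.2 | 0.025 | 0.094 | 0.254 |
| 0.3 | 0.025 | 0.156 | 0.496 |

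If the same bias runs against the coated device and the true effect is 0.5, power at *q* = 1 is 0.738, 0.496 and 0.255. An operator who always starts on the same anatomical side gives *q* near 0.5, because side is randomised. One who always starts with the same letter gives *q* of 1 or 0 for as long as the letters keep their meaning.

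**5. Can recording order replace the guide-catheter rule?** No. The mean difference is δ + *o* − δ*c* in coated-first subjects and δ − *o* in coated-second subjects. Their contrast, 2*o* − δ*c*, mixes the two effects.

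**The case against.** The strongest reply is that the answer may lie outside these documents. Protocol 11.2 requires UP Devices to be used according to the instructions for use, and sites are trained on them (17.2.1). Those instructions may already call for a fresh guide catheter on each side. This stands: the text shows a gap in the plan, not that reuse or contamination happens. The limit on retraction in step 10 is also an existing control, although it concedes that drug can come off there.

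On order, the reply is that confounding needs two things the documents do not show: sites working by letter, and a first/second-side effect that lasts to Day 30. Anaesthesia is a weak candidate for such an effect, since it is completed before the envelope is opened. This also stands, and it is why the order figures above show sensitivity and do not predict what will happen.

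Several stronger readings are tempting but unsupported.

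- A reader might infer that carry-over could produce a false win. It cannot, because it only pulls the difference towards zero.
- A reader might take the dose not delivered under the 90% delivery assumption in Protocol 7.4 as the amount transferred. That percentage is a simulation input. Undelivered drug is not transferred drug, and what stays on the balloon is discarded with it.
- A reader might extend the carry-over route to the lightwire and handle. The lightwire is inserted through the device from its proximal end, and nothing shows the handle touching the coating.
- A reader might see bias in the permitted range of balloon hold times. That range applies equally to both devices and would add noise, not bias, unless hold time differed systematically by device. Nothing suggests it does.

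**Conclusion.** The concern holds as a gap in the plan. A site can follow the protocol exactly and still bring a drug-exposed guide catheter to the control ostium, or treat the two devices in the same order in every subject.

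- **Carry-over** costs power and understates the effect. At an assumed 10% loss when the coated side goes first, power falls from 0.90 to 0.87 (half of subjects) or 0.83 (all). The documents give no figure for the loss, and the instructions for use may already prevent it.
- **Order tied to device** threatens validity in either direction. With complete linkage and assumed order effects of 0.1 to 0.3 grade in the drug's favour, the false-win probability is 0.095 to 0.496 instead of 0.025. With balanced order it stays at 0.025. Both the linkage and the effect size are assumptions.

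The change is worth making because the whole primary comparison rests on the side difference and the protection is cheap.

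**What to change.** - **Protocol 11.2 (randomized cohort) and 17.3.2:** require a separate guide catheter for each side, as is already done for the UP Device. Check this against the instructions for use first; if they already require it, repeat the requirement in the protocol.
- **Same sections:** fix the treatment order independently of device code, for example by anatomical side and the same in every subject. Order then coincides with left/right, but both are balanced against device by the 1:1 randomisation.
- **Case report form:** record which side was dilated first. For any subjects already treated, operative reports (listed among source documents in Protocol 17.4) may show it.
- **SAP 10.3.2:** add a sensitivity analysis of the primary endpoint by order. One form regresses the within-subject difference on an order indicator coded ±1, with the intercept as the order-adjusted effect.

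The cost is protocol and SAP wording, one data field, and at most one extra guide catheter per randomized subject (about 70). No visit is added, and the required sample size of 53 evaluable subjects and its power of 0.901 are unchanged.
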